APPENDIX VI-A: PHARMACOKINETIC STUDY FORM FOR PATIENTS ON DL1

COG Pt ID # _____

Cycle 1, Day 1 Date: _____

Please do not write patient names on this form or on samples.

Patient Weight: _____ kg

Flotetuzumab Dose Level: _____ nanograms/kg/day Flotetuzumab Total Daily Dose: _____ nanograms

Blood samples (2 – 3 ml) will be collected in SST tubes at the following time points during Cycle 1 (\pm 10 min) for patients that do NOT require dose interruptions: Day 1 (prior to infusion), Days 3 – 7 (30 minutes prior to syringe change and dose escalation), Day 8 (24 hours after Day 7 syringe change and final dose escalation) and on Days 12, 15, 19, 22, 27, and 29 (at any time). For patients that require dose interruptions during Cycle 1, PK samples should be drawn according to when the patient reaches certain dose levels (see chart below). **NOTE:** Patients \leq 23 kg should only have 2 ml of blood drawn per sample.

Additional blood samples will also be collected at the following time points on the patient's last day of protocol therapy (\pm 10 min): 30 minutes, 1 hour, 2, hours, 4 hours, 8 hours, and 24 hours after the end of infusion.

Record the exact time the samples are drawn during Cycle 1, as well as the exact time infusion begins and ends on Days 1 and 29 (respectively), and the exact time of syringe change on days in which PK samples are collected. Also record the exact time the sample is drawn on the patient's last day of protocol therapy, the exact time infusion ends on the patient's last day of protocol therapy, the patient's last cycle number, and the day in the 29 day cycle in which the patient stopped protocol therapy.

Cycle 1

Blood Sample No.	Planned Day of Collection*	Actual Day of Collection	Scheduled Collection Time	Actual Date Sample Collected	Actual Time Sample Collected (24-hr clock)
1	Day 1	Day 1	Prior to flotetuzumab infusion	/ /	____:____
	Flotetuzumab Infusion on Day 1		Date: / / Infusion Start Time: _____	Time: _____	
2	Day 3	Day _____	30 mins prior to syringe change and dose escalation	/ /	____:____
	Syringe Change from 60 to 100 ng/kg/day		Date: / / Time of Syringe Change: _____	Time: _____	
3	Day 4	Day _____	30 mins prior to syringe change and dose escalation	/ /	____:____
	Syringe Change from 100 to 200 ng/kg/day		Date: / / Time of Syringe Change: _____	Time: _____	
4	Day 5	Day _____	30 mins prior to syringe change and dose escalation	/ /	____:____
	Syringe Change from 200 to 300 ng/kg/day		Date: / / Time of Syringe Change: _____	Time: _____	
5	Day 6	Day _____	30 mins prior to syringe change and dose escalation	/ /	____:____
	Syringe Change from 300 to 400 ng/kg/day		Date: / / Time of Syringe Change: _____	Time: _____	
6	Day 7	Day _____	30 mins prior to syringe change and dose escalation	/ /	____:____
	Syringe Change from 400 to 500 ng/kg/day		Date: / / Time of Syringe Change: _____	Time: _____	
7	Day 8	Day 8	24 hrs after syringe change for final dose escalation	/ /	____:____
8	Day 12	Day 12	Any time	/ /	____:____
9	Day 15	Day 15	Any time	/ /	____:____
10	Day 19	Day 19	Any time	/ /	____:____
11	Day 22	Day 22	Any time	/ /	____:____
12	Day 27	Day 27	Any time	/ /	____:____

THIS PROTOCOL IS FOR RESEARCH PURPOSES ONLY, SEE PAGE 1 FOR USAGE POLICY

13	Day 29	Day 29	Any time	/ /	____:____
Flotetuzumab Infusion on Day 29		Date: ____ / ____		Infusion End Time: ____ : ____	

*Assuming patient follows the dosing schedule in [Section 5.1](#) and requires no dose interruptions.

Signature: _____
(site personnel who collected samples)

Date: _____

Cycle #: _____					
Blood Sample No.	Time Point	Scheduled Collection Time	Actual Date Sample Collected	Actual Time Sample Collected (24-hr clock)	
Flotetuzumab Infusion on Patient's Last Day of Therapy		Date: ____ / ____ / ____	Infusion End Time: ____ : ____		
14	Day __	30 mins after end of infusion	/ /	____:____	
15	Day __	1 hr after end of infusion	/ /	____:____	
16	Day __	2 hrs after end of infusion	/ /	____:____	
17	Day __	4 hrs after end of infusion	/ /	____:____	
18	Day __	8 hrs after end of infusion	/ /	____:____	
19	Day __	24 hrs after end of infusion	/ /	____:____	

One copy of this Pharmacokinetic Study Form should be uploaded into RAVE. A second copy should be sent with the samples to the address listed in [Section 8.2.6](#). See [Section 8.2](#) for detailed guidelines for packaging and shipping PK samples.

Signature: _____
(site personnel who collected samples)

Date: _____

THIS PROTOCOL IS FOR RESEARCH PURPOSES ONLY, SEE PAGE 1 FOR USAGE POLICY

APPENDIX VI-B: PHARMACOKINETIC STUDY FORM FOR PATIENTS ON DL-1

COG Pt ID # _____ Cycle 1, Day 1 Date: _____

Please do not write patient names on this form or on samples.

Patient Weight: _____ kg

Flotetuzumab Dose Level: _____ nanograms/kg/day Flotetuzumab Total Daily Dose: _____ nanograms

Blood samples (2 – 3 ml) will be collected in SST tubes at the following time points during Cycle 1 (\pm 10 min) for patients that do NOT require dose interruptions: Day 1 (prior to infusion), Days 4, 6, and 8 (30 minutes prior to syringe change and dose escalation), Day 9 (24 hours after Day 8 syringe change and final dose escalation) and on Days 13, 17, 21, 25, and 29 (at any time). For patients that require dose interruptions during Cycle 1, PK samples should be drawn according to when the patient reaches certain dose levels (see chart below). **NOTE:** Patients \leq 23 kg should only have 2 ml of blood drawn per sample.

Additional blood samples will also be collected at the following time points on the patient's last day of protocol therapy (\pm 10 min): 30 minutes, 1 hour, 2, hours, 4 hours, 8 hours, and 24 hours after the end of infusion.

Record the exact time the sample are drawn during Cycle 1, as well as the exact time infusion begins and ends on Days 1 and 29 (respectively), and the exact time of syringe change on days in which PK samples are collected. Also record the exact time the sample is drawn on the patient's last day of protocol therapy, the exact time infusion ends on the patient's last day of protocol therapy, the patient's last cycle number, and the day in the 29 day cycle in which the patient stopped protocol therapy.

Cycle 1

Blood Sample No.	Planned Day of Collection*	Actual Day of Collection	Scheduled Collection Time	Actual Date Sample Collected	Actual Time Sample Collected (24-hr clock)
1	Day 1	Day 1	Prior to flotetuzumab infusion	/ /	_____ : _____
2	Day 4	Day _____	Flotetuzumab Infusion on Day 1 Date: _____ / _____ / _____ Infusion Start Time: _____ : _____	/ /	_____ : _____
3	Day 6	Day _____	Syringe Change from 60 to 100 ng/kg/day Date: _____ / _____ / _____ Time of Syringe Change: _____ : _____	/ /	_____ : _____
4	Day 8	Day _____	Syringe Change from 100 to 200 ng/kg/day Date: _____ / _____ / _____ Time of Syringe Change: _____ : _____	/ /	_____ : _____
5	Day 9	Day 9	Syringe Change 200 to 300 ng/kg/day Date: _____ / _____ / _____ Time of Syringe Change: _____ : _____	/ /	_____ : _____
6	Day 13	Day 13	24 hrs after Day 8 syringe change and final dose escalation	/ /	_____ : _____
7	Day 17	Day 17	Any time	/ /	_____ : _____
8	Day 21	Day 21	Any time	/ /	_____ : _____
9	Day 25	Day 25	Any time	/ /	_____ : _____
10	Day 29	Day 29	Any time	/ /	_____ : _____
			Flotetuzumab Infusion on Day 29 Date: _____ / _____ / _____ Infusion End Time: _____ : _____		

*Assuming patient follows the dosing schedule in [Section 5.1](#) and requires no dose interruptions.

(continued next page)

THIS PROTOCOL IS FOR RESEARCH PURPOSES ONLY, SEE PAGE 1 FOR USAGE POLICY

Signature: _____
(site personnel who collected samples)

Date: _____

Cycle #: _____					
Blood Sample No.	Time Point	Scheduled Collection Time	Actual Date Sample Collected	Actual Time Sample Collected (24-hr clock)	
Flotetuzumab Infusion on Patient's Last Day of Therapy		Date: ___ / ___ / ___	Infusion End Time: ___ : ___ : ___		
11	Day ___	30 mins after end of infusion	___ / ___ / ___	___	___ : ___
12	Day ___	1 hr after end of infusion	___ / ___ / ___	___	___ : ___
13	Day ___	2 hrs after end of infusion	___ / ___ / ___	___	___ : ___
14	Day ___	4 hrs after end of infusion	___ / ___ / ___	___	___ : ___
15	Day ___	8 hrs after end of infusion	___ / ___ / ___	___	___ : ___
16	Day ___	24 hrs after end of infusion	___ / ___ / ___	___	___ : ___

One copy of this Pharmacokinetic Study Form should be uploaded into RAVE. A second copy should be sent with the samples to the address listed in [Section 8.2.6](#). See [Section 8.2](#) for detailed guidelines for packaging and shipping PK samples.

Signature: _____
(site personnel who collected samples)

Date: _____

THIS PROTOCOL IS FOR RESEARCH PURPOSES ONLY, SEE PAGE 1 FOR USAGE POLICY

APPENDIX VI-C: PHARMACOKINETIC STUDY FORM FOR PATIENTS ON DL2COG Pt ID # _____
Please do not write patient names on this form or on samples.

Patient Weight: _____ kg

Flotetuzumab Dose Level: _____ nanograms/kg/day Flotetuzumab Total Daily Dose: _____ nanograms

Blood samples (2 – 3 ml) will be collected in SST tubes at the following time points during Cycle 1 (\pm 10 min) for patients that do NOT require dose interruptions: Day 1 (prior to infusion), Days 3 – 8 (30 minutes prior to syringe change and dose escalation), Day 9 (24 hours after Day 7 syringe change and final dose escalation) and on Days 13, 17, 21, 25, and 29 (at any time). For patients that require dose interruptions during Cycle 1, PK samples should be drawn according to when the patient reaches certain dose levels (see chart below). **NOTE:** Patients \leq 23 kg should only have 2 ml of blood drawn per sample.

Additional blood samples will also be collected at the following time points on the patient's last day of protocol therapy (\pm 10 min): 30 minutes, 1 hour, 2, hours, 4 hours, 8 hours, and 24 hours after the end of infusion.

Record the exact time the samples are drawn during Cycle 1, as well as the exact time infusion begins and ends on Days 1 and 29 (respectively), and the exact time of syringe change on days in which PK samples are collected. Also record the exact time the sample is drawn on the patient's last day of protocol therapy, the exact time infusion ends on the patient's last day of protocol therapy, the patient's last cycle number, and the day in the 29 day cycle in which the patient stopped protocol therapy.

Cycle 1

Blood Sample No.	Planned Day of Collection	Actual Day of Collection	Scheduled Collection Time	Actual Date Sample Collected	Actual Time Sample Collected (24-hr clock)
1	Day 1	Day 1	Prior to flotetuzumab infusion	/ /	____:____
			Flotetuzumab Infusion on Day 1 Date: _____	Infusion Start Time: _____	_____
2	Day 3	Day _____	30 mins prior to syringe change and dose escalation	/ /	____:____
			Syringe Change from 100 to 200 ng/kg/day Date: _____	Time of Syringe Change: _____	_____
3	Day 4	Day _____	30 mins prior to syringe change and dose escalation	/ /	____:____
			Syringe Change from 200 to 300 ng/kg/day Date: _____	Time of Syringe Change: _____	_____
4	Day 5	Day _____	30 mins prior to syringe change and dose escalation	/ /	____:____
			Syringe Change from 300 to 400 ng/kg/day Date: _____	Time of Syringe Change: _____	_____
5	Day 6	Day _____	30 mins prior to syringe change and dose escalation	/ /	____:____
			Syringe Change from 400 to 500 ng/kg/day Date: _____	Time of Syringe Change: _____	_____
6	Day 7	Day _____	30 mins prior to syringe change and dose escalation	/ /	____:____
			Syringe Change from 600 to 600 ng/kg/day Date: _____	Time of Syringe Change: _____	_____
7	Day 8	Day _____	30 mins prior to syringe change and dose escalation	/ /	____:____
			Syringe Change from 700 to 800 ng/kg/day Date: _____	Time of Syringe Change: _____	_____
8	Day 9	Day 9	24 hrs after Day 8 syringe change and final dose escalation	/ /	____:____
9	Day 13	Day 13	Any time	/ /	____:____
10	Day 17	Day 17	Any time	/ /	____:____
11	Day 21	Day 21	Any time	/ /	____:____
12	Day 25	Day 25	Any time	/ /	____:____

THIS PROTOCOL IS FOR RESEARCH PURPOSES ONLY, SEE PAGE 1 FOR USAGE POLICY

13	Day 29	Day 29	Any time	/ /	__ : __
		Flotetuzumab Infusion on Day 29	Date: ___ / ___ / ___	Infusion End Time: ___ : ___	

*Assuming patient follows the dosing schedule in [Section 5.1](#) and requires no dose interruptions.

Signature: _____
(site personnel who collected samples)

Date: _____

Cycle #: _____					
Blood Sample No.	Time Point	Scheduled Collection Time	Actual Date Sample Collected	Actual Time Sample Collected (24-hr clock)	
Flotetuzumab Infusion on Patient's Last Day of Therapy		Date: ___ / ___ / ___	Infusion End Time: ___ : ___		
14	Day __	30 mins after end of infusion	/ /	__ : __	
15	Day __	1 hr after end of infusion	/ /	__ : __	
16	Day __	2 hrs after end of infusion	/ /	__ : __	
17	Day __	4 hrs after end of infusion	/ /	__ : __	
18	Day __	8 hrs after end of infusion	/ /	__ : __	
19	Day __	24 hrs after end of infusion	/ /	__ : __	

One copy of this Pharmacokinetic Study Form should be uploaded into RAVE. A second copy should be sent with the samples to the address listed in [Section 8.2.6](#). See [Section 8.2](#) for detailed guidelines for packaging and shipping PK samples.

Signature: _____
(site personnel who collected samples)

Date: _____

THIS PROTOCOL IS FOR RESEARCH PURPOSES ONLY, SEE PAGE 1 FOR USAGE POLICY

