Flotetuzumab 500 nanograms/kg/day							X				
Flotetuzumab 600 nanograms/kg/day								X			
Flotetuzumab 700 nanograms/kg/day									X	X	

*can be given between Days -6 and 0

All Cohorts, Cycles 2+

	Day 1	Day 2-28	29
IT cytarabine*	X		End of flotetuzumab infusion
Flotetuzumab at Cycle 1 target dose	X	X	

*Patients may receive an optional dose of IT cytarabine during subsequent cycles on Day 1 or with bone marrow evaluations at the discretion of the treating physician.

If a treatment-free interval > 3 days occurs between any 2 cycles, the subsequent cycle will require step-up dosing. If a treatment-free interval > 3 days occurs between any 2 cycles, the Study Chair must be notified and the subsequent cycle dosing schedule must be discussed.

IT Cytarabine Age-based dosing:

Age (yrs)	Dose
< 1	20 mg
1-1.99	30 mg

THIS PROTOCOL IS FOR RESEARCH PURPOSES ONLY, SEE PAGE 1 FOR USAGE POLICY

2-2.99	50 mg
≥ 3	70 mg

Infusion Related Reaction/Cytokine Release Syndrome Prophylaxis prior to each subsequent cycle and for prolonged interruptions:

Prophylaxis is required prior to subsequent cycles if the treatment-free interval is greater than 24 hours. Prophylaxis is also recommended following any interruption in cycles that last >24 hours. For interruptions in cycles that last <24 hours, prophylaxis can be given at the discretion of the treating physician.

Acetaminophen: 10 – 15 mg/kg/dose (max: 650 mg/dose) IV or PO
Day 1: 30 minutes prior to starting flotetuzumab infusion, then q4-6h prn

Diphenhydramine: 0.5 – 1 mg/kg/dose (max: 50 mg) IV or PO
Day 1: 30 minutes prior to flotetuzumab infusion, then q6-8h prn

Ranitidine: 1 mg/kg/dose IV (max single dose: 50 mg) or 2 mg/kg/dose PO (max single dose: 150 mg); or equivalently dosed H2 receptor antagonist (e.g., famotidine)
Day 1: 30 minutes prior to starting flotetuzumab infusion, then q8h (IV) or q12h (PO) prn

Dexamethasone

Day 1: 5 mg/m²/dose (max single dose: 5 mg) IV or PO once 30 minutes prior to starting flotetuzumab infusion, then 5 mg/m²/dose (max single dose: 5 mg) IV or PO given 12 hours later (total daily dose: 10 mg/m²)

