5.3 Dose Escalation Schema

5.3.1 Inter-Patient Escalation

The starting dose will be 500 nanograms/kg/day (DL1) with dose levels for subsequent groups of patients as follows:

Dose Level	Dose (nanograms/kg/day)
-1	300
1*	500
2	700

* Starting Dose Level

THIS PROTOCOL IS FOR RESEARCH PURPOSES ONLY, SEE PAGE 1 FOR USAGE POLICY

There will be no planned escalations beyond Dose Level 2 (700 nanograms/kg/day), as previous pediatric Phase 1 studies have rarely defined a MTD greater than 160% of the adult MTD. If estimated clearance is high in this pediatric study population, we will consider amending the protocol to allow further dose escalation to 900 nanograms/kg/day.

If the MTD has been exceeded at the first dose level, then the subsequent cohort of patients will be treated at a dose of 300 nanograms/kg/day (Dose Level -1). If Dose Level -1 is not well tolerated, further de-escalation will not occur. The study will be closed to accrual.

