		6	500 nanograms/kg/day		
		7	600 nanograms/kg/day		
		8-28	700 nanograms/kg/day		

THIS PROTOCOL IS FOR RESEARCH PURPOSES ONLY, SEE PAGE 1 FOR USAGE POLICY

Ht _____ cm

Wt _____ kg

BSA _____ m²

Dose Level _____ nanograms/kg/day

Date Due	Date Given	Day	IT ARAC _____ mg	Flotetuzumab 30 nanograms/kg/ day ng	Flotetuzumab 100 nanograms/kg/ day ng	Flotetuzumab 200 nanograms/kg/ day ng	Flotetuzumab 300 nanograms/kg/ day ng	Flotetuzumab 400 nanograms/kg/ day ng	Flotetuzumab 500 nanograms/kg/ day ng	Flotetuzumab 600 nanograms/kg/ day ng	Flotetuzumab 700 nanograms/kg/ day ng	Studies
Enter calculated dose above and actual dose administered below												
		Pre-	_____ mg									a – d, f – q, u – x
		1		_____ ng								r – t
		2			_____ ng							
		3				_____ ng						e
		4					_____ ng					e
		5						_____ ng				e
		6							_____ ng			e
		7								_____ ng		e
		8									_____ ng	e, r, s
		9									_____ ng	e
		10									_____ ng	
		11									_____ ng	
		12									_____ ng	
		13									_____ ng	e
		14									_____ ng	
		15									_____ ng	r
		16									_____ ng	
		17									_____ ng	e
		18									_____ ng	
		19									_____ ng	
		20									_____ ng	
		21									_____ ng	e
		22									_____ ng	r
		23									_____ ng	
		24									_____ ng	
		25									_____ ng	e
		26									_____ ng	
		27									_____ ng	
		28									_____ ng	
		29										e, i, j, q, r, v, w, y

THIS PROTOCOL IS FOR RESEARCH PURPOSES ONLY, SEE PAGE 1 FOR USAGE POLICY

Required Observations in Cycle 1**All baseline studies must be performed prior to starting protocol therapy unless otherwise indicated below.**

- a. History. Prior to Cycle 1 and every week during Cycle 1.
- b. Physical exam (including VS). Prior to Cycle 1 and every week during Cycle 1.
- c. Performance Status. Prior to Cycle 1.
- d. CBC/diff/platelets. Prior to Cycle 1 and twice weekly during Cycle 1. If patients have Grade 4 neutropenia then CBCs should be checked at least every other day until recovery to Grade 3 or until meeting the criteria for dose limiting toxicity.

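### The DL2 pharmacokinetic form labels the Day 7 and Day 8 dose steps differently from the protocol's own DL2 schedule, names a dose the protocol does not plan, and dates the final escalation two ways

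*Combined protocol and SAP*

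**What the plan says.** The Section 5.1 Cycle 1 table for the highest level steps up daily and ends with "Flotetuzumab 700 nanograms/kg/day" from Day 8 onward. Days 6 and 7 are at 500 and 600. The DL2 delivery map in Appendix IV-C gives the same three figures. Section 5.3.1 states: "There will be no planned escalations beyond Dose Level 2 (700 nanograms/kg/day". It then allows that an amendment to 900 might be considered if clearance turns out to be high. Section 5.3.2 confines within-patient escalation at DL2 to the first 8 days of Cycle 1.

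The DL2 PK form in Appendix VI-C has six pre-printed syringe-change rows. The Day 6 row reads "Syringe Change from 400 to 500 ng/kg/day". The next two read "Syringe Change from 600 to 600 ng/kg/day" (sample 6, Day 7) and "Syringe Change from 700 to 800 ng/kg/day" (sample 7, Day 8). The form's introduction describes the Day 9 sample as taken "24 hours after Day 7 syringe change and final dose escalation". Row 8 of the same form, Section 8.2.2, the labelling table in Section 8.2.5 and item e of Appendix IV-C all place that escalation on Day 8.

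Two timing rules apply. Patients who keep to the schedule are sampled by calendar day, half an hour before the syringe change on each of Days 3 to 8 (Section 8.2.2). For patients with interruptions in Cycle 1, the form says: "PK samples should be drawn according to when the patient reaches certain dose levels (see chart below". The chart it refers to is the one containing the two rows in question.

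**The concern.** A form that sites fill in during step-up at the highest dose level should match the dosing schedule. This one shows a Day 7 step with no change in dose, followed by a Day 8 step to a figure found nowhere else in the protocol.

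The labels have a function. After an interruption, the calendar day no longer identifies the dose step, and the form tells the site to use the printed dose instead. For such a patient, sample 6 is keyed to a change that is not a change, and sample 7 to a step outside the plan. Interruptions are foreseeable: Section 6.3.1.3 requires the infusion to be stopped for a Grade 3 reaction, and Section 2.3.1 reports dose-limiting Grade 3 reactions in 3 of 9 adults at 700 ng/kg/day.

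At stake are the timing and labelling of a few PK samples in some DL2 patients, for a secondary aim (Section 1.2.1). In addition, a document in site hands names a dose above the planned ceiling.

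**Working it through.** No sample-size or error-rate calculation applies. The check compares each printed step with the step implied by the dosing schedule.

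**Step 1. DL2 rows.** The schedule column is the previous day's dose to that day's dose, from Section 5.1, with Appendix IV-C agreeing on every day.

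| Sample | Planned day | Schedule (ng/kg/day) | Appendix VI-C label | Agree? |
|---|---|---|---|---|
| 2 | 3 | 100 to 200 | 100 to 200 | yes |
| 3 | 4 | 200 to 300 | 200 to 300 | yes |
| 4 | 5 | 300 to 400 | 300 to 400 | yes |
| 5 | 6 | 400 to 500 | 400 to 500 | yes |
| 6 | 7 | 500 to 600 | 600 to 600 | no |
| 7 | 8 | 600 to 700 | 700 to 800 | no |

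Agreement is 4 of 6. This locates the disagreement. It does not decide which passage should change.

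**Step 2. Internal check of the form alone.** In a step-up chain, each row should start where the previous row ended. Rows 2 to 5 do. Row 5 ends at 500 and row 6 starts at 600. Row 6 ends at 600 and row 7 starts at 700. The chain breaks twice, so the form is inconsistent even without reference to Section 5.1.

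**Step 3. The other two forms.** The same comparison gives 5 of 5 for DL1 (Appendix VI-A) and 3 of 3 for DL-1 (Appendix VI-B, where the extracted text displaces rows by one). Overall, 5 + 3 + 4 = 12 of 14 labels agree. Both mismatches are in adjacent rows of the DL2 form.

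**Step 4. Day 9 text.** 24 hours after a Day 7 change falls on Day 8, so the introduction cannot describe a Day 9 sample. The same phrase appears in the DL1 form, where the final step is on Day 7 and the sample on Day 8. That suggests text carried over from one form to the other.

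**Step 5. Size of the figure.** 800/700 = 1.143, so the printed figure is 14% above the highest planned level.

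**Step 6. Who is affected.** Under the Section 11.3 table, a level may be left after 2 patients (if both have DLT) and otherwise runs to at most 6. Section 11.2.2 allows expansion to 12, and Section 11.1 allows up to 6 PK-expansion patients, who would be at DL2 only if that dose were taken forward. The labels would therefore be on the forms of 2 to 6 evaluable patients, and of at most 12 + 6 = 18. The timing effect is limited to those with a Cycle 1 interruption that disturbs these steps. The documents give no rate for that.

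**Step 7. What a misread label could do.** Suppose, as an assumption, that an analyst took the printed starting dose as the dose running when the sample was drawn. Relative to the schedule, sample 6 would be assigned 600/500 = 1.20 times the dose and sample 7 would be assigned 700/600 = 1.17 times. With clearance estimated as infusion rate over steady-state concentration, those two samples would overstate clearance by about 20% and 17%. This is a bound on a misuse, not an expected bias.

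**The case against.** The strongest reply is that this is a clerical matter with safeguards around it, and most of that stands.

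- A reader might infer that samples 6 and 7 have no valid trigger for anyone at DL2. The documents do not support that. Section 8.2.2, Appendix IV-C and the form itself give patients on schedule a trigger by day. Even after an interruption, a careful site could work out that samples 6 and 7 precede the two escalations between the matching 400-to-500 row and the final one. The form does not say so, however, and the rule it does state points to the printed doses.
- A reader might infer that sites are being told to give 800 ng/kg/day. They are not. The form records sampling, the dosing passages agree with each other, and the dose level is assigned through the enrolment system (Section 3.10).
- A reader might infer that dose-exposure data are corrupted. Section 8.2.1 pairs concentrations with each patient's dosing history, Appendix IV-C records the dose actually given each day, the PK form captures actual times, and tube labels use the day (Section 8.2.5). Nothing says that the pre-printed label enters the analysis, so the 20% and 17% above would require those records to be ignored.
- A reader might infer that the recommended dose is threatened. Sections 11.1 to 11.3 decide it on DLT counts, and Section 11.5 keeps PK descriptive. The one PK-linked decision is the possible amendment to 900 in Section 5.3.1.

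A machine-reading error is also possible. It is less likely than an error in the form, because several digits in two adjacent rows would have to be misread while the other 12 labels came through consistently. The source page should still be checked.

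**Conclusion.** The inconsistency is real and confined to one form: two of six DL2 step labels, plus one phrase on the Day 9 sample. The Day 9 discrepancy is the weaker part, because four other places agree on Day 8 and the phrase is impossible as written.

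Every DL2 patient's form carries the labels. Sample timing is at risk only for samples 6 and 7 in patients with dose interruptions, a number the documents do not allow one to estimate. The realistic harm is a mistimed or mislabelled PK sample, a data query, and a site-facing document that names an unplanned dose. There is no support for a dosing error, a lost PK dataset or an effect on the dose-escalation decision.

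This is an internal inconsistency that should be corrected before the form is used at DL2. It does not reach the level of a must-fix flaw in the design. The conclusion assumes that the extracted labels match the printed page.

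**What to change.** First, check the Day 7 and Day 8 syringe-change rows against the source page of Appendix VI-C. If they read as extracted, the sponsor should reconcile those rows and the Day 9 wording in the introduction with the DL2 schedule in Section 5.1, the sampling times in Section 8.2.2 and the delivery map in Appendix IV-C, so that all four give the same steps on the same days. Reissue the form before DL2 opens. If any DL2 forms have already been completed, compare samples 6 to 8 with the delivery map before PK analysis.

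The cost is the correction of one form. The design, sample size and analysis do not change.
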